3.1.2. Secondary Objectives

- To determine the safety and tolerability of the combination of rituximab and pembrolizumab in relapsed/refractory WM
- To assess the depth of response to rituximab and pembrolizumab and duration of response
- To determine the time to best response and time to next therapy
- To determine the effect of rituximab and pembrolizumab on quality of life

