3.2. Trial Endpoints

3.2.1. Primary end-points:

- Percentage of patients achieving an overall response rate (defined as complete response (CR), very good partial response (VGPR), partial response (PR) or minor response (MR) i.e. a greater than 25% reduction in the serum IgM level) at 24 weeks post commencing treatment

3.2.2. Secondary end-points:

- Safety and tolerability of pembrolizumab and rituximab as assessed by the frequency of serious and non-serious adverse events, graded according to CTCAE v5.0
- Complete response (CR) rate at 24 weeks post commencing treatment (see appendix 4)
- Very good partial response (VGPR) rate at 24 weeks post commencing treatment (see appendix 4)
- Time to maximal response, as determined by the time of registration to the maximal disease response
- Time to next treatment, as determined by the time from registration to the next line of therapy
- Progression free survival (PFS) at 1 and 2 years
- Overall survival (OS) at 1 and 2 years
- Change in quality of life (QoL) at 24 weeks post commencing treatment

3.2.3. Exploratory endpoints:

- Assessment of PD-1 and PD-L1/ PD-L2 expression by fluorescence in situ hybridisation (FISH) and immunohistochemistry (IHC).
- IHC to assess baseline and on-treatment changes to distribution and composition of immune response cells in the microenvironment
- Analysis of baseline biopsies to elucidate potential mechanisms of action of tumour response
- Assessment of treatment outcome according to tumour genotype, as determined by sequencing assays for MYD88^{L265P} and CXCR4 mutations
- Correlation of bone marrow response with reduction in serum IgM level.
- Quantification of bone marrow involvement by morphologic assessment of trephine and flow cytometric assessment of aspirate for MRD

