9.2. Assessments during Treatment

Patients should be seen prior to and during each cycle of trial treatment. Investigations should be performed in line with the Schedule of Events table in appendix 2.

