9.2.2. Disease response assessments

In addition to the assessments before each treatment cycle (section 9.2.1), disease response is to be assessed at 12 weeks (+/- 3 days), 24 weeks (+/- 3 days) and 1 year (+/- 2 weeks) after commencing treatment. The following assessments should be performed at these time points:

- Concurrent medication assessment
- Adverse event assessment
- Full blood count (including red blood cell (RBC), haemoglobin (Hb), white blood cell (WBC) absolute neutrophil count (ANC), absolute lymphocyte count (ALC), haematocrit and platelets)
- Biochemistry (including bicarbonate, uric acid, albumin, alkaline phosphatase (ALP), alanine/aspartate transaminase (ALT/AST), total bilirubin, calcium, creatinine, potassium, sodium, glucose, urea, and estimated glomerular filtration rate (eGFR), U&E, liver function tests (LFT))
- Quality of life questionnaire – EORTC QLQ-C30 (only performed at week 24)
- Serum IgM, IgG and IgA
- Serum paraprotein
- Serum free light chain (SFLC)
- Serum immunofixation (only to be performed if paraprotein not detectable)
- CT scan of neck, chest, abdomen and pelvis (NCAP) (CT scans to be performed at week 24 and 1 year after commencing treatment in patients with evidence of measurable/nodal disease on baseline scan)
- Bone marrow aspirate and trephine (only to be performed at week 24 and year 1 after commencing treatment).

Research samples – week 24 and 1 year only (see section 10 for further details) – all samples below are optional and therefore should only be obtained from patients who have given consent

- Bone marrow aspirate
- Peripheral blood

Response at these time points should be assessed using the International Working Group for WM response criteria (see appendix 4).

Patients will remain on treatment for a maximum of 1 year or until disease progression, discontinuation due to unacceptable toxicity or any other reason (whichever occurs sooner).

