9.3. Assessments after Disease Progression

Following disease progression patients will be assessed at 5 months (+4 weeks) after the date of treatment discontinuation, over the phone or at a standard hospital visit for the purposes of:

- Adverse event assessment

Patients are then followed up for the trial annually from the date of progression for the following:

- Remission status assessment (investigations as per local protocols)

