Progression free survival will be analysed using Kaplan-Meier survival analyses, with the time calculated from the date of registration to the date of progression/death. Patients who are alive and progression free will be censored at the date last seen. The median (if applicable), rates at 1 and 2 years and a Kaplan-Meier curve will be presented.

Overall survival

Overall survival will be analysed using Kaplan-Meier survival analyses, with the time calculated from the date of registration to the date of death. Patients who are alive will be censored at the date last seen. The median (if applicable), rates at 1 and 2 years and a Kaplan-Meier curve will be presented.

Quality of life

Quality of life is assessed using the QLQ-30 questionnaire at baseline and at week 24. Differences between baseline and week 24 will be compared using paired t-tests and changes between baseline and week 24 may also be compared to historical data from the R2W trial.

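### The week-24 quality-of-life analysis leaves out patients who progress early and possibly those who stop early, because no questionnaire is clearly scheduled for them

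*Combined protocol and SAP*

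**What the plan says.** The secondary objective in protocol section 3.1.2 is "To determine the effect of rituximab and pembrolizumab on quality of life". The matching endpoint in section 3.2 is "Change in quality of life (QoL) at 24 weeks post commencing treatment". Neither is limited to patients still on treatment.

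Section 17.2.2 states "Quality of life is assessed using the QLQ-30 questionnaire at baseline and at week 24", and then "Differences between baseline and week 24 will be compared using paired t-tests". It adds that the changes may be compared with historical data from the R2W trial. It gives no quality-of-life analysis population, missing-data rule, completion report or sensitivity analysis.

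The questionnaire schedule is as follows:

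- **Baseline (9.1):** QLQ-C30 before treatment starts.
- **On treatment (9.2, which opens "Patients should be seen prior to and during each cycle of trial treatment"):** the 9.2.2 response visits fall at 12 weeks, 24 weeks and 1 year from the start of treatment. The form is listed there as "Quality of life questionnaire – EORTC QLQ-C30 (only performed at week 24" (quotation cut before the closing bracket).
- **After progression (9.3):** "Following disease progression patients will be assessed at 5 months (+4 weeks) after the date of treatment discontinuation", for adverse events only, then annual remission status.
- **After completing or stopping treatment without progression (9.4):** a detailed day-60 list, an adverse-event contact at 5 months, then annual remission status. No questionnaire appears.
- **Appendix 1:** the quality-of-life row is marked at pre-registration and at the 24-week response visit only.

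Section 15.2 keeps patients who stop treatment in the trial for follow-up and analysis unless they withdraw consent.

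**The concern.** Leaving treatment before week 24 is foreseeable. Progression ends therapy (8.2), and so do several toxicities (8.4, 8.5) and a need for plasmapheresis after cycle 2 (8.4.6). A patient can therefore leave the part of the schedule that contains the only follow-up questionnaire while remaining in the trial. The missing form then results from the visit schedule, not from patient refusal, and its absence is tied to the course of disease or toxicity.

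Section 17.2.1 deals with this risk for response: a patient with a missing week-24 response who has progressed or died counts as a non-responder. Quality of life has no counterpart. In a single-arm trial no control group would show the selection, and any comparison with R2W would carry it over.

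**Working it through.** **1. The plan's own figures.** The documents state no sample size, standard deviation, effect size or expected completion for quality of life, so there is nothing to reproduce for this endpoint. The primary design does reproduce: 23 or more responses in 42, with rates of 40% and 60%, gives exact one-sided alpha 0.0375 and power 0.803. It does not use the questionnaire.

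**2. Who has a week-24 form, read from the schedule**

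| Patient's course before week 24 | Governing section | Week-24 QLQ-C30 |
|---|---|---|
| Still on treatment, including doses withheld | 9.2.2 | Scheduled |
| Progressed | 9.3 | None listed |
| Stopped without progression | 9.4, perhaps also 9.2.2 | None listed in 9.4; unclear whether the 9.2.2 visit still applies |
| Died | – | Not obtainable |

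**3. Effect on the mean.** Let *m* be the share of living patients without a week-24 form, and let *gap* be the mean change in those with a form minus the mean change in those without.

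All-patient mean = (1 − m) × mean(with form) + m × mean(without form) = mean(with form) − m × gap.

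The paired analysis reports mean(with form), so it overstates by m × gap. The number of pairs is 42 × (1 − m), rounded. Both *m* and *gap* are assumptions.

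| m | Pairs | Gap 0 | Gap 5 | Gap 10 | Gap 20 |
|---|---|---|---|---|---|
| 10% | 38 | 0 | 0.5 | 1.0 | 2.0 |
| 20% | 34 | 0 | 1.0 | 2.0 | 4.0 |
| 30% | 29 | 0 | 1.5 | 3.0 | 6.0 |
| 40% | 25 | 0 | 2.0 | 4.0 | 8.0 |

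Entries are QLQ-C30 points of overstatement. A negative gap would reverse the sign.

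**4. Effect on the test.** Suppose the true all-patient mean change is 0 and the test is two-sided at 0.05 (section 17.2.2 states neither level nor sidedness). The chance of a significant improvement is nominally 2.5%. With a gap it comes from the noncentral t distribution with noncentrality (m × gap / SD) × √n. With an assumed SD of change of 20:

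- m 20%, gap 10: (2/20) × √34 = 0.58, giving 8.2%.
- m 30%, gap 10: (3/20) × √29 = 0.81, giving 11.9%.
- m 30%, gap 20: (6/20) × √29 = 1.62, giving 34.5%.
- gap 0: 2.5% at any m, with only the loss of pairs.

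For m 30% and gap 10, varying the SD from 15 to 25 moves the chance from 17.9% to 9.1%.

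**The case against.** The strongest reply is that the week-24 visit is counted from the start of treatment and is not tied to treatment status. The endpoint is defined the same way, and in Appendix 1 the footnote on treatment duration is attached to the cycle column, not to the 24-week column. Nothing says the day-60 list in 9.4 replaces a response visit still due. For patients who stop without progression this stands: the protocol is ambiguous, and a site could properly collect the form. It is weaker for progressors, who have their own section with a short list. Even so, two possible readings mean collection may differ between sites.

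A reader might also infer that the result will describe only patients who tolerated treatment and did not progress. The documents do not support that. Many toxicities lead to withholding or continuing treatment (8.4), and those patients still complete the form. So do patients whose progression is first found at the week-24 visit.

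Nor do the documents establish upward bias. Under Appendix 3, progression can be a confirmed IgM rise without symptoms, and a patient who stopped for toxicity may have recovered by week 24. The direction is plausible but remains an assumption.

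Finally, this is one secondary endpoint in an uncontrolled trial, with no power statement or decision threshold. Even complete forms would give only a before-after change. That limits the weight of the point but does not remove it.

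**Conclusion.** The point holds in limited form. There is a gap in the schedule for patients who progress before week 24 and an ambiguity for those who stop for other reasons. The paired analysis excludes anyone without a week-24 form, and section 17.2.2 does not acknowledge this.

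The reported change would be too favourable if the excluded patients do worse. The range of 0.5 to 8 points rests wholly on the assumed missing share and gap, because the documents supply neither. The finding is a cheap and worthwhile clarification of a stated endpoint. It has no bearing on the rule of 23 responses in 42.

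**What to change.** **Schedule (9.2.2, 9.3, 9.4 and Appendix 1).** State that the week-24 QLQ-C30, counted from the start of treatment, is collected from every living patient who started treatment and has not withdrawn consent, whether or not they have progressed or stopped. It can be returned by post or completed at a routine visit.

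**Analysis (17.2.2).** Analyse all patients with baseline and week-24 forms regardless of treatment status. Show those still on treatment separately. Report completion with reasons for missing forms, including deaths. Apply the same rules to the trial's side of any R2W comparison, and say which R2W patients contribute.

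**What not to do.** Do not put a form completed at discontinuation in place of the week-24 value in the main analysis. It measures a different time, often near peak toxicity or progression, and could bias the result downwards. At most it belongs in a sensitivity analysis.

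**Cost.** A few extra paper forms, no added clinic visit, and a protocol amendment with its approvals (18.4). Some forms will be completed on later therapy, which the separate display makes visible. Forms for patients already past week 24 cannot be recovered, and deaths before week 24 remain missing under any schedule.

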17.3. Interim analyses

There will be no formal interim analyses however toxicities will be monitored closely throughout the trial (see section 12.6). In addition to periodic reviews, an IDMC meeting will be triggered as a result of trial-treatment related deaths as outlined below.

An IDMC review will be triggered if the number of treatment related deaths exceeds 10% of the number of patients recruited.

Number of Patients (N)	Number of treatment related deaths needed for IDMC trigger (more than 10% of N)
10	2
15	2
20	3
25	3
30	4
35	4

18. ETHICAL AND REGULATORY CONSIDERATIONS

This trial will adhere to the conditions and principles of GCP as outlined in the Medicines for Human Use (Clinical Trials) Regulations 2004 (SI 2004/1031), as amended.

In conducting the trial, the Sponsor, UCL CTC and sites shall comply with the protocol and with all relevant guidance, laws and statutes, as amended from time to time, applicable to the performance of clinical trials and research including, but not limited to:

- The UK Policy Framework for Health and Social Care Research, issued by the Health Research Authority
- Human Rights Act 1998
- Data Protection Act 2018
- General Data Protection Regulation (EU)2016/679 (GDPR)
- Freedom of Information Act 2000
- Human Tissue Act 2004
- Medicines for Human Use (Clinical Trials) Regulations (SI 2004/1031), and subsequent amendments
- Medicines Act 1968
- Good Manufacturing Practice

18.1. Ethical Approval

The trial will be conducted in accordance with the World Medical Association Declaration of Helsinki entitled 'Ethical Principles for Medical Research Involving Human Subjects' (1996 version) and in accordance with the terms and conditions of the ethical approval given to the trial.

The trial has received a favourable opinion from the London – London West Research Ethics Committee (REC) and Health Research Authority (HRA) approval for conduct in the UK.

UCL CTC will submit Annual Progress Reports to the REC, commencing one year from the date of ethical approval for the trial.

Favourable opinion will also be obtained in all participating countries outside the UK in compliance with all local laws, statutes and requirements.

18.2. Regulatory Approval

A Clinical Trial Authorisation (CTA) has been granted for the trial.

The trial will be conducted at approved trial sites in accordance with the trial protocol and the terms of the CTA granted by the MHRA.

18.3. Site Approvals

Evidence of assessment of capability and capacity by the Trust/Health Board R&D for a trial site must be provided to UCL CTC. Sites will only be activated when all necessary local approvals for the trial have been obtained.

18.4. Protocol Amendments

UCL CTC will be responsible for gaining ethical and regulatory approval, as appropriate, for amendments made to the protocol and other trial-related documents. Once approved, UCL CTC will ensure that all amended documents are distributed to sites as appropriate.

Site staff will be responsible for acknowledging receipt of documents and for implementing all amendments promptly.

18.5. Patient Confidentiality & Data Protection

Patient identifiable data, including initials and date of birth will be required for the registration process and will be provided to UCL CTC. UCL CTC will preserve patient confidentiality and will not disclose or reproduce any information by which patients could be identified. Data will be stored in a secure manner and UCL CTC trials are registered in accordance with the Data Protection Act 2018 and GDPR with the Data Protection Officer at UCL.

Patient identifiable data, including initials and date of birth will be provided to the HMDS in order to process the sample. HMDS will preserve patient confidentiality and will not disclose or reproduce any information by which patients could be identified.

19.2. Indemnity

University College London holds insurance against claims from participants for injury caused by their participation in the clinical trial. Participants may be able to claim compensation if they can prove that UCL has been negligent. However, as this clinical trial is being carried out in a hospital, the hospital continues to have a duty of care to the participant of the clinical trial. University College London does not accept liability for any breach in the hospital's duty of care, or any negligence on the part of hospital employees. This applies whether the hospital is an NHS Trust or otherwise.

Participants may also be able to claim compensation for injury caused by participation in this clinical trial without the need to prove negligence on the part of University College London or another party. Participants who sustain injury and wish to make a claim for compensation should be advised to do so in writing in the first instance to the Chief Investigator, who will pass the claim to the Sponsor's Insurers, via the Sponsor's office.

Hospitals selected to participate in this clinical trial shall provide clinical negligence insurance cover for harm caused by their employees and a copy of the relevant insurance policy or summary shall be provided to University College London, upon request.

20. FUNDING

MSD Ltd are supporting the central coordination of the trial through UCL CTC, translational research at HMDS, and supplying pembrolizumab free of charge for use in the trial.

Research A costs will be reimbursed to sites as per the finance section of the mNCA.

21. PUBLICATION POLICY

The results of the PembroWM trial will be presented at relevant conferences and published in a peer reviewed journal. The primary publication from the trial will be written by the TMG. Authors will include the CI, TMG members, representatives of UCL CTC including the trial coordinator and trial statistician, and PIs at sites that make a significant contribution to patient recruitment.

Abstracts and papers will be reviewed by MSD Ltd prior to submission in accordance with the requirements of the Trial Drug Supply Agreement.

The ISRCTN/Clinicaltrials.gov number of the trial and the funder reference number will be quoted in all publications.

Sites may not publish any data pertaining to PembroWM patients without prior written permission from the TMG.

Data generated from the PembroWM trial will be the property of UCL as Trial Sponsor.

APPENDIX 1: QUICK REFERENCE GUIDE TO PATIENT VISITS

	Pre-registration (within 28 days of full registration unless otherwise stated)	D1 of each cycle (- 3days) ^a	Response at 12 weeks (+/- 3days)	Response at 24 weeks (+/- 3days)	Response at 1 year (+/- 2weeks)	D+60 post treatment discontinuation (+/- 3days) ^b	5 months post treatment discontinuation (+4weeks)	Annual FU until EoT declared (pt who complete treatment/ discontinue for reasons other than progression)	Annual FU until EoT declared (following disease progression)
Eligibility checklist	X								
Demographics and Medical History (see 9.1)	X								
Physical examination including performance status and observations (see 9.1 & 9.2)	X	X				X			
Height	X								
Weight	X	X				X			
Quality of Life Questionnaire	X			X					
Lymph node biopsy ^c	X								
Adverse Event reporting ^d					X				
Concomitant Medications					X				
ECG ^e	X	X							
Hepatitis B and C serology	X								

HIV serology	X									
FBC	X	X	X	X	X	X				
U+E	X	X	X	X	X	X				
LFT	X	X	X	X	X	X				
LDH	X						X			
B2 microglobulin	X									
Serum IgM, IgG, IgA	X	X	X	X	X					
Serum paraprotein	X	X	X	X	X					
Serum immunofixation ^f		X	X	X	X					
Direct antiglobulin test	X									
TSH, glucose, ACTH	X	X					X			
Pregnancy test (serum or urine)	X	X								
Amylase	X	X					X			
CT scan ^g	X			X	X					
Serum SFLC	X		X	X	X					
Bone marrow aspirate and trephine ^h	X			X	X					
MyD88 and CXCR4 mutation status by NGS ⁱ	X									
Flow for B-cell and plasma cell phenotype ^j	X			X	X					
Remission status and assessment of late toxicity ^k									X	X

- a: patients will remain on treatment for a maximum of 1 year or until disease progression, discontinuation due to unacceptable toxicity or any other reason (whichever occurs sooner).
- b: patients who complete treatment or discontinue treatment early for reasons other than progression should be followed at day 60 post treatment discontinuation (+/-3 days). They will then be followed up at 5 months and annually thereafter until the last patient completes 2 years of follow up.
- c: Lymph node biopsy if nodal disease. Biopsy within 28 days prior to C1D1 preferred. If not possible, then historical biopsy tissue will be obtained and sent for exploratory analysis at HMDS (see section 10 for further details). Note: this only applies to patients who have given consent to optional samples being sent to HMDS.
- d: Adverse events are to be recorded between informed consent and 5 months after the last IMP administration. AESI and SAES are to be reported to UCL CTC within 24 hours of awareness (see section 12 for details),
- e: A 12 lead ECG should be performed for all patients pre-registration and prior to commencing each cycle of pembrolizumab. Further ECGs should be performed as clinically indicated.
- f: Serum immunofixation to be performed only if paraprotein no longer detectable.
- g: CT scan of neck, chest, abdomen and pelvis (NCAP) to be performed pre-registration (within 28 days prior to starting treatment). CT scan (NCAP) to be repeated at 24 weeks and 1 year post commencing treatment only if nodal disease on baseline assessment. Thereafter, only to be done if clinical concerns of nodal progression. If no measurable disease was documented at baseline, then a CT NCAP should be performed as clinically indicated.
- h: Bone marrow aspirate and trephine to be performed pre-registration (within 28 days prior to starting treatment) and at week 24 and 1 year to determine response. Samples to be analysed locally. Additionally, for consenting patients bone marrow samples to be sent to HMDS for exploratory analysis (see section 10 for further details).
- i: Peripheral blood sample for MyD88 and CXCR4 analysis will be sent at screening to HMDS for exploratory analysis from consenting patients (see section 10 for further details).
- j: Peripheral blood sample for flow cytometry for B-cell/plasma cell phenotypes will be sent to HMDS for exploratory analysis from consenting patients (see section 10 for further details).
- k: Remission status as per local policy.

